If all pertinent information is unavailable with the initial submission, once the additional information is available **do not submit a new report**. Rather, go to the original email that was sent to the STRC and using that email "reply to all". Entitle this new email "**Amendment** for (list date of event and patient ID)" this will avoid duplications of the same event. List the additional information being reported. This information needs to be entered into WISER as well. To do this, go to the Subject console and click SAEs on the left column. Click on the appropriate SAE number that needs updating. Then click update. This will allow additional information to be added

Acronyms

AE – Adverse Event

STRC-Safety and Toxicity Review Committee

SAE-Serious Adverse Event

WFBCCC – Wake Forest Baptist Comprehensive Cancer Center

NCI-National Cancer Institute

WISER –Wake Integrated Solution for Enterprise Research

Screen Shots:

The following screen shots come from the SAE Console within the Subject Console in WISER.

**Secondary versus Tertiary Wound Closure in High Risk
Gynecologic Abdominal Surgical Incisions
CCCWFU # 04418**

Screen Shot 1:

Protocol No.: CCCWFU04418

Protocol Status: OPEN TO ACCRUAL

Subject Name: [REDACTED]

Subject Status: ON TREATMENT

Sequence No.: [REDACTED]

Switch Subject Type here to search

Summary

Demographics

Consent

Eligibility

On Study

Treatment

Follow-Up

SAEs

Payments

Deviations

Documents/Info

Protocols

MRN

CRA Console

PC Console

Subject Demographics

MRN: [REDACTED]

Last Name: [REDACTED]

First Name: [REDACTED]

Birth Date: [REDACTED]

Gender: F

Race: White

Subject Comments

Additional Subject Identifiers

Identifier Type: Identifier Identifier Owner: No information entered

Contact Information

Name: [REDACTED]	Primary	Address	City	State	ZIP	County	Country	Phone No.	Email Address
------------------	---------	---------	------	-------	-----	--------	---------	-----------	---------------

Emergency Contacts

Name	Primary	Address	City	State	ZIP	County	Country	Phone No.	Email Address
------	---------	---------	------	-------	-----	--------	---------	-----------	---------------

No information entered

Copyright © 2003-2018 Forte Research Systems. All rights reserved.

Screen Shot 2:

Protocol No.: CCCWFU04418

Protocol Status: OPEN TO ACCRUAL

Subject Name: [REDACTED]

Subject Status: ON TREATMENT

Sequence No.: [REDACTED]

Switch Subject Type here to search

Summary

Demographics

Consent

Eligibility

On Study

Treatment

Follow-Up

SAEs

Payments

Deviations

Documents/Info

Protocols

MRN

CRA Console

PC Console

No Records Found

New

Copyright © 2003-2018 Forte Research Systems. All rights reserved.

**Secondary versus Tertiary Wound Closure in High Risk
Gynecologic Abdominal Surgical Incisions
CCCWFWU # 04418**

Screen Shot 3:

Protocol No.: CCCWFU04418
MRN: [REDACTED]

Protocol Status: OPEN TO ACCRUAL Subject Name: [REDACTED]

Subject Status: ON TREATMENT Sequence No.: [REDACTED]

Subject Not Complete

Subject SAE Details

Event Date: [REDACTED] Event End Date: [REDACTED] Reported Date: [REDACTED] Reported By: [REDACTED]

6 Event Number: [REDACTED] 7 Event Description: [REDACTED] 8 Reporting Date: [REDACTED] 9 Events By: [REDACTED]

10 Treatment: [REDACTED] 11 Consent Form Change Required: [REDACTED]

12 Event Details: [REDACTED] 13 Adverse Event Details: [REDACTED]

14 Action Date: [REDACTED] 15 Grade Severity: [REDACTED] 16 Therapy: [REDACTED]

Comments: [REDACTED] 3000 characters remaining

Source: [REDACTED] Attribution: [REDACTED]

17 DLT - Dose Limiting Toxicity

Action: [REDACTED] 18 Action Date: [REDACTED]

DSMB Reviewed: [REDACTED] 19 Grade Severity: [REDACTED]

IRG Approved: [REDACTED] 20 Therapy: [REDACTED]

Notified CTD/CDM: [REDACTED] 21 Comments: [REDACTED]

Notified CIO: [REDACTED] 22 Action Date: [REDACTED]

Notified FDC: [REDACTED] 23 Grade Severity: [REDACTED]

Notified SIS: [REDACTED] 24 Therapy: [REDACTED]

Notified Sponsor: [REDACTED] 25 Comments: [REDACTED]

Notified STIC: [REDACTED] 26 Action Date: [REDACTED]

Team Reviewed: [REDACTED] 27 Grade Severity: [REDACTED]

28 Therapy: [REDACTED]

Additional SAE Details

Identifier Type: [REDACTED] Identifier: [REDACTED] Identifier Owner: [REDACTED]

No information entered

Complete and Lock Submit Clear Close

Screen Shot 4:

Protocol No.: CCCWFU04418
MRN: [REDACTED]

Protocol Status: OPEN TO ACCRUAL Subject Name: [REDACTED]

Subject Status: OFF STUDY (Expired) Sequence No.: [REDACTED]

Subject Not Complete

Subject SAE Details

Event Date: [REDACTED] Event End Date: [REDACTED] Reported Date: [REDACTED] Reported By: [REDACTED]

1 Event Number: [REDACTED] 2 Event Description: [REDACTED] 3 Reporting Date: [REDACTED] 4 Events By: [REDACTED]

5 Treatment: [REDACTED] 6 Consent Form Change Required: [REDACTED]

7 Event Details: [REDACTED] 8 Adverse Event Details: [REDACTED]

9 Action Date: [REDACTED] 10 Grade Severity: [REDACTED] 11 Therapy: [REDACTED]

Comments: [REDACTED] 3000 characters remaining

Source: [REDACTED] Attribution: [REDACTED]

12 DLT - Dose Limiting Toxicity

Action: [REDACTED] 13 Action Date: [REDACTED]

DSMB Reviewed: [REDACTED] 14 Grade Severity: [REDACTED]

IRG Approved: [REDACTED] 15 Therapy: [REDACTED]

Notified CTD/CDM: [REDACTED] 16 Comments: [REDACTED]

Notified CIO: [REDACTED] 17 Action Date: [REDACTED]

Notified FDC: [REDACTED] 18 Grade Severity: [REDACTED]

Notified SIS: [REDACTED] 19 Therapy: [REDACTED]

Notified Sponsor: [REDACTED] 20 Comments: [REDACTED]

Notified STIC: [REDACTED] 21 Action Date: [REDACTED]

Team Reviewed: [REDACTED] 22 Grade Severity: [REDACTED]

23 Therapy: [REDACTED]

Additional SAE Details

Identifier Type: [REDACTED] Identifier: [REDACTED] Identifier Owner: [REDACTED]

No information entered

Supporting Documents

Document ID: [REDACTED] File Name: [REDACTED] Description: [REDACTED] Version Date: [REDACTED] Created Date: [REDACTED] Last Edit: [REDACTED] Delete: [REDACTED]

No Records Found.

Appendix D – Baseline Data Collection Form

Instructions: Fill this form out to collect baseline data

1. BMI: ____ . ____

2. ASA Class

- II
- III
- IV
- V
- VI

3. Medical Comorbidities

- Acute Myocardial Infarction
- History of Myocardial Infarction
- Congestive Heart Failure
- Peripheral Vascular Disease
- Cerebrovascular Disease
- Chronic Obstructive Pulmonary Disease (COPD)
- Dementia
- Paralysis (Hemiplegia or Paraplegia)
- Diabetes
- Diabetes with Complications
- Renal Disease
- Mild Liver Disease
- Moderate/Severe Liver Disease
- Peptic Ulcer Disease
- Rheumatologic Disease
- AIDS

(Additional)

4. Surgical History

- a. Has the patient had previous surgery? Yes No
- b. If Yes, please describe:

5. Tobacco Use (Check all that apply):

Smoking Status:

- Current Every day smoker,
- Current some day smoker,
- Former smoker,
- Heavy Tobacco smoker,
- Light Tobacco smoker,
- Never assessed,
- Never Smoker,
- Passive smoke exposure-
- Never smoker,
- Smoker-current status unknown,
- Unknown if ever smoked

Start date (mm/dd/yyyy): ____/____/_____

Quit date (mm/dd/yyyy): ____/____/_____

Types (Check all that apply):

- Cigarettes,
- Pipe,
- Cigars,
- E-cig/Vapor w/nicotine,
- E-cig/Vapor w/o

Pack/Day: ____

Years: ____

Smokeless Tobacco: Current user, Former user, Never used, Unknown

Types: Snuff, Chew

Quit date (mm/dd/yyyy): ____/____/_____

Comment:

Appendix E – Surgery Form

Instructions: Use this form to fill out relevant surgery information

1. Date of Surgery (mm/dd/yyyy): ____ / ____ / ____

2. Wound Measurements

- a. Subcutaneous depth: ____ cm
- b. Length: ____ . ____ cm
- c. Width: ____ . ____ cm

3. Procedure

- a. Colon bundle used? Yes No
- b. Antibiotic use: Yes No
 - i. If Yes, name type, dose and frequency:
 - ii. Type: _____
 - iii. Dose: _____
 - iv. Frequency: _____
- c. Is the antibiotic type appropriate? Yes No

4. Length of Surgery

- a. Surgery Start Time (hh:mm): ____ : ____
- b. Surgery Stop (hh:mm): ____ : ____
- c. Time total time (hh:mm): ____ : ____

5. Wound Class

II

III

IV

6. Intraoperative Complications (free text):

Appendix F - Wound Form

Visit: 2 weeks 4 weeks 3 months

Date of encounter (mm/dd/yyyy): ____/____/_____

1. Infection: Yes No

If yes, date infection occurred: (mm/dd/yyyy): ____/____/_____

2. Did Wound Dehiscence occur? Yes No

If yes, date: (mm/dd/yyyy): ____/____/_____

Physician's assessment of why dehiscence occurred:

3. Percentage of wound healing: _____%

4. Day of hospital discharge (mm/dd/yyyy): ____/____/_____

5. Post-surgery date wound is closed

(mm/dd/yyyy): ____/____/_____

6. Is the wound closed on POD # 30? Yes No

7. Wound Complications (free text):

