2.0 Objectives

2.1 Primary Objective

2.1.1 To compare the percentage of patients whose wound remained closed on postoperative day #30 after tertiary closure compared to historical controls who underwent secondary wound closure. We are primarily looking at time to wound closure. We will be able to abstract this information from the postoperative clinic visit notes from patients in the "historical control" cohort. We will identify 20 patients with characteristics described in the inclusion criteria of this study who underwent laparotomy with secondary wound closure during the calendar year 2018.

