5.0 Outcome Measures

5.1 Primary Outcomes

- 5.1.1 The percentage of patients whose wound is closed on postoperative day # 30 after tertiary wound closure compared to historical controls who underwent secondary wound closure.

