5.2 Secondary Outcomes

- 5.2.1 The proportion of SSI using a tertiary closure technique compared to historical controls receiving a secondary wound closure.
- 5.2.2 The length of stay as defined by the time from surgery to discharge as compared to historical controls receiving a secondary wound closure.
- 5.2.3 The proportion of patients that return within 30 days of surgery.
- 5.2.4 The quality of life in patients receiving a tertiary wound closure. It is expected that tertiary closure will be superior to secondary closure. The time to closure with the tertiary approach should be much shorter. It is unknown if wounds closed in a tertiary manner will remain closed. That was our rationale for choosing wound closure at 30 days as the primary endpoint. Differences in quality of life between the two approaches are also unknown. We have submitted an abstract from a chart review of 5 patients who have undergone tertiary closure. We are looking to expand this cohort of patients to generate more quantitative data.

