10.0 Adverse Events List and Reporting Requirements

10.1 Adverse Event List for Tertiary Closure

10.1.1 Infection

As a result of enrollment onto this trial, there is a risk of developing a wound infection. This infection could be minor (skin redness). A wound infection could also involve the deeper tissues underneath the skin. If that occurs, the incision is typically re-opened and the deeper tissues are cleaned, irrigated and packed with a dressing. Rarely, a serious wound infection causes you to develop a fever or generalized infection. Treatment of a more serious wound infection could involve the following: re-admission to the hospital, intravenous antibiotics or additional surgery.

Enrolled patients will be at medium to high risk for wound complications in general. Wound complications usually occur within the first 30 days of surgery. Incisional hernia is a more "long-term" complication of a surgical wound. This complication can occur up to 1 year after surgery. Enrolled patients will be monitored carefully for wound complications using our standard care approach for patients with medium to high risk for wound complications.

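### The objective asks whether tertiary wounds stayed closed to day 30, but the outcome and the wound form record only day-30 status, so a wound re-opened and closed again counts as a success

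*Combined protocol and SAP*

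**What the plan says.** All references are to the combined protocol and SAP.

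- **Objective (2.1.1)** compares the percentage of patients "whose wound remained closed on postoperative day #30 after tertiary closure" with historical controls. It adds that time to closure is of primary interest.
- **Outcome (5.1.1)** is "The percentage of patients whose wound is closed on postoperative day # 30 after tertiary wound closure".
- **Rationale (5.2.4):** "It is unknown if wounds closed in a tertiary manner will remain closed". The next sentence makes this the reason for choosing closure at 30 days.
- **Sample size and analysis (6.1, 6.3)** use a third wording, closure within 30 days.
- **Infection (10.1.1):** infection may be minor. If deeper tissues are involved, "the incision is typically re-opened and the deeper tissues are cleaned, irrigated and packed with a dressing".
- **Wound form (Appendix F)**, completed at 2 weeks, 4 weeks and 3 months. Item 2 is "2. Did Wound Dehiscence occur? Yes No", with a date and the physician's view of the cause. Item 5 is "5. Post-surgery date wound is closed", with one date. Item 6 is "6. Is the wound closed on POD # 30? Yes No".

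No section says how to classify a tertiary wound that is opened after approximation and is closed again by POD 30.

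**The concern.** Staying closed and being closed on a given day are different properties. The first is the question the plan says it wants answered. The second is what it records and tests.

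They part company for a wound that is approximated, opened because of deep infection, packed, and shut again before POD 30. That wound did not stay closed, and after re-opening it was handled much like the comparator, yet it is credited to tertiary closure.

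Time to closure has a related weakness. If item 5 keeps the date of bedside approximation (day 4 to 7 under 4.3.3), a wound opened later still carries an early closure date.

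What is at stake is the meaning of the tertiary closure figure, and whether the trial can report directly on durability.

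**Working it through.** **1. The three wordings applied to the same wounds** (days are illustrative)

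| Course | Stayed closed (2.1.1) | Closed on POD 30 (5.1.1, item 6) | Closure within 30 days (6.1, 6.3) |
|---|---|---|---|
| Tertiary: approximated day 5, never opened | Yes | Yes | Yes |
| Tertiary: approximated day 5, opened day 10, shut by day 28 | No | Yes | Yes |
| Tertiary: approximated day 5, opened day 10, still open day 30 | No | No | Could be yes |
| Control: left open, filled in by day 25 | Does not apply | Yes | Yes |

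The second row is the gap. Replacing the 6.1/6.3 wording with strict POD-30 status corrects the third row but leaves the second. The fourth row shows that staying closed cannot be the between-group measure, because control wounds start open.

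**2. What the records can recover**

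Appendix F gives infection and dehiscence dates, percentage of healing and free-text complications at each visit. The adverse event log (Appendix H) has start and end dates and a code for a required intervention. None of these is linked to item 6. Deliberate re-opening may or may not be entered as dehiscence, a term the plan does not define. Reconstruction is therefore possible in part, not assured.

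**3. Size**

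One patient of 20 is 1/20 = 5 percentage points. The number affected is

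20 × (infection rate) × (share re-opened) × (share shut again by POD 30).

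- *Infection rate*, from the classification table in section 1.0: clean-contaminated 5–6%, contaminated 20–25%, dirty 30–40%. Times 20, these give 1.0–1.2, 4–5 and 6–8 patients if all 20 were in that class. The case mix is not given. High-risk class II should exceed its class baseline, but by an unstated amount.
- *Share re-opened*: 10.1.1 describes this for deeper infection only. Section 1.0 puts about 2/3 of gynecologic surgical site infections as superficial, so about 1/3 is a rough guide and 1 is a ceiling.
- *Share shut again*: not in the documents. I assume 0 to 0.5.

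Results:

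- Ceiling (all dirty wounds, every infection re-opened, half re-closed): 20 × 0.40 × 1 × 0.5 = 4 patients, 20 points.
- Same with 1/3 re-opened: 20 × 0.40 × 1/3 × 0.5 = 1.3 patients, about 7 points.
- Class II baseline, every infection re-opened, half re-closed: 20 × 0.05 × 0.5 = 0.5 patient.
- Re-closure near 0, as 6.1 expects for wounds left open: about 0.

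If every wound is closed on POD 30, the two tertiary figures (with Clopper-Pearson 95% CI) would be:

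| Patients re-opened and re-closed | Closed on POD 30 | Stayed closed |
|---|---|---|
| 0 | 20/20 = 100% (83–100%) | 20/20 = 100% (83–100%) |
| 1 | 20/20 = 100% (83–100%) | 19/20 = 95% (75–100%) |
| 2 | 20/20 = 100% (83–100%) | 18/20 = 90% (68–99%) |
| 4 | 20/20 = 100% (83–100%) | 16/20 = 80% (56–94%) |

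**4. Power**

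Section 6.1 claims more than 90% with 20 versus 100 patients, two-sided 0.05, expecting near 100% versus near 0%. Taking these as 0.90–0.99 versus 0.01–0.10 (assumption), the pooled-variance normal approximation, exact enumeration of the chi-squared test and Fisher's exact test all give about 100%. The claim reproduces.

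Stress test at 60% versus 10%, well below the ceiling case:

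- pooled p = (12 + 10)/120 = 0.1833
- null SE = √(0.1833 × 0.8167 × (1/20 + 1/100)) = 0.0948
- alternative SE = √(0.24/20 + 0.09/100) = 0.1136
- power = Φ((0.50 − 1.96 × 0.0948)/0.1136) = Φ(2.77) = 99.7%

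With 20 controls, the number in 2.1.1, the same rates give 94% by this approximation, 95% by exact chi-squared and 91% by Fisher. The 20-versus-100 control count needs reconciling separately and does not alter this point.

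**The case against.** Status on POD 30 regardless of what happened in between is a legitimate endpoint, and it is the only one both groups share. Making never re-opened the primary measure would give the two arms different definitions. This stands, and the fix keeps POD-30 status as the comparison.

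The path may also be rare. Packing is the only management of a re-opened wound that the plan describes, and 6.1 expects almost no open wound to close by POD 30. Re-suturing is not mentioned anywhere. The pilot summary in section 1.0 reports no infection or wound complication at sixty days in six class III/IV wounds. All of this stands, though with 0 of 6 the exact 95% upper limit is 1 − 0.025^(1/6) = 46%, and a limited re-opening might close sooner than a whole incision.

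One can also read the objective's wording as status on that day. That is possible, but the rationale in 5.2.4 points to durability, and an ambiguous primary endpoint needs settling either way.

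Two stronger inferences are not supported. A reader might conclude that the tertiary rate is inflated by 5 to 20 points. That needs every patient to be class III or IV, every infection to be re-opened, and a re-closure rate for which the documents give no figure. A reader might also conclude that the form makes durability unanswerable. The dated infection, dehiscence, healing and adverse event entries allow partial reconstruction, and section 6 specifies no time-to-closure analysis that would carry the item 5 date into a result.

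**Conclusion.** The point holds as a mismatch of definition and recording. The plan poses a durability question, scores day-30 status, and does not explicitly record the event that separates the two.

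The effect is 5 percentage points per affected patient. The plausible number is 0 to a few of 20: near 0 if open wounds rarely close by POD 30 and none is re-sutured, and 4 only under the ceiling assumptions above. The direction favours tertiary closure.

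The power statement and, at the anticipated rates, the expected test result do not change. What changes is the tertiary closure figure and what it may be said to show. The conclusion rests on the ordinary meaning of staying closed, supported by 5.2.4. This is an inexpensive improvement worth making, not an error in any figure of the plan.

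**What to change.** 1. Keep wound closed on POD 30 as the between-group comparison, and use that one wording in 2.1.1, 5.1.1, 6.1, 6.3 and Appendix F.
2. Pre-specify a separate tertiary-arm estimate with an exact 95% CI: the proportion approximated and continuously closed to POD 30. Count any dehiscence, surgical re-opening, re-closure or return to packing or VAC after approximation as failure, whatever the day-30 status.
3. In Appendix F, widen item 2 to dehiscence or surgical re-opening, with date and how it was managed.
4. Split item 5 into date first approximated and date finally closed, and use the final date for time to closure.

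The cost is two changed form items, answered from the same examination and chart, and a few sentences in the plan. No visit or treatment changes. The durable-closure figure may be lower than the POD-30 figure, and because it describes one arm only it cannot be compared with the controls.

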4.2 Study Activities Table

	Pre-Study	At Surgery	2 weeks post-surgery (+/- 5 days)	4 weeks post-surgery (+/- 5 days)	3-month Follow-up (+/- 5 days)
Informed consent	X				
Demographics	X				
Medical history					
• Surgical History	X				
Concurrent meds	X				
Physical exam	X				X
Vital signs	X				X
Wound Characteristics					
• Wound Class		X			
• Wound Depth					
• Wound Size					
Duration of Surgery	X	X			
Wound Assessment			X	X	X
Quality of life (SF-36)	X		X	X	X
CBC w/diff, platelets	X				
Comprehensive Metabolic Panel	X				
B-HCG (urine or serum)	X				
Adverse event evaluation		X	X	X	X

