6.3 Analysis of Primary Outcome

The chi-squared test will be used to compare the proportions of wound closure within 30 days between the experimental group (i.e., patients receiving a tertiary wound closure) and the historical control group (i.e., patients receiving a secondary wound closure). Logistic regression models will be used when confounding variables such as age will be adjusted. Wound closure status is the outcome measure. Experimental group is the covariate of interest.

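### The primary endpoint is wound status on POD 30, but 7 of the 11 permitted days for the nearest visit come earlier, and no rule derives that status alike in both groups

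*Combined protocol and SAP*

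**What the plan says.** **Endpoint.** Section 5.1.1 defines a fixed-day status: "The percentage of patients whose wound is closed on postoperative day # 30 after tertiary wound closure". Section 2.1.1 adds the idea of durability: "To compare the percentage of patients whose wound remained closed on postoperative day #30 after tertiary closure". Section 5.2.4 gives the reason for choosing day 30: it is not known whether wounds closed by the tertiary technique stay closed. Section 6.3 is worded differently. Its test is to "compare the proportions of wound closure within 30 days between the experimental group", and section 6.1 also refers to closure by day 30.

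**Tertiary group.** The table in section 4.2 schedules wound assessments at 2 weeks, at "4 weeks post-surgery (+/- 5 days" and at "3-month Follow-up (+/- 5 days". The same Wound Form serves all three visits. Item 6 asks "Is the wound closed on POD # 30" and offers Yes or No. Item 5 asks for the "Post-surgery date wound is closed", and item 2 records dehiscence with a date.

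**Controls.** Section 2.1.1 relies on the records of 2018 patients: "We will be able to abstract this information from the postoperative clinic visit notes from patients". It gives no timing for those visits, no definition of closure and no rule for unknown status.

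**The concern.** An endpoint tied to one day needs either an examination on or just after that day, or a stated rule for deriving the status from dated records. The plan has neither. Item 6 has no option for a visit that takes place before POD 30, and nothing says which of the three forms supplies the analysed answer.

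For tertiary wounds, approximated on day 4 to 7 (section 4.3.3), the open question is whether they re-open. Section 10.1.1 says wound complications usually occur in the first 30 days. Taking a day 23 answer as POD 30 status leaves out a week of the period that the endpoint was chosen to cover. For controls, a wound open at one note and closed at the next, with POD 30 in between, has no determinable status unless a closure date was written down.

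The two groups are thus ascertained by different means, a prospective form and retrospective notes. Neither the chi-squared test nor covariate adjustment in section 6.3 removes a difference of that kind.

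**Working it through.** **1. Visit days against POD 30** (section 4.2; surgery taken as day 0)

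- 2-week visit: 14 ± 5 = days 9 to 19. All precede POD 30.
- 4-week visit: 28 ± 5 = days 23 to 33, which is 11 days. Days 23 to 29 precede POD 30 (7 of 11 = 64%), day 30 is on it (1 of 11 = 9%), and days 31 to 33 follow it (3 of 11 = 27%). The nominal day, 28, is before POD 30.
- 3-month visit: taking 3 months as 90 days, 90 ± 5 = days 85 to 95, or 55 to 65 days after POD 30.

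These are shares of permitted days. They are shares of patients only if visits spread evenly over the window, which the plan does not say.

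**2. The plan's own power figure.** Section 6.1 claims more than 90% power, two-sided 0.05, for 20 patients against 100 controls at close to 100% and close to 0%. Section 2.1.1 gives 20 controls, so both counts are shown. Power of the uncorrected chi-squared test by exact binomial enumeration:

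| Closure, tertiary v control | 20 v 100 | 20 v 20 |
|---|---|---|
| 99% v 1% | 100% | 100% |
| 95% v 5% | 100% | 100% |
| 90% v 10% | 100% | 100% |
| 80% v 20% | 99.98% | 98.2% |
| 70% v 30% | 92.8% | 71.3% |

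The claim reproduces. The 80% v 20% row is also what a true 100% v 0% would become if one patient in five were misread in each group towards the other. The test survives that with either control count. If three in ten were misread (70% v 30%), it survives with 100 controls but not comfortably with 20.

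**3. Effect on the estimates.** One misread patient moves a proportion by 1/n: 1/20 = 5 points, 1/100 = 1 point. If k controls are indeterminate and no other control closed, coding alone moves the control proportion from 0 to k/n. With assumed counts, 4/20 or 20/100 gives 0 to 20%, and 6/20 or 30/100 gives 0 to 30%.

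**4. Effect on inference if the true difference is small** (illustration, all rates assumed). Let true closure be 50% in both groups. Let a share m of open tertiary wounds be recorded closed, and the same share of closed control wounds be recorded open. The recorded rates are 0.5 + 0.5m and 0.5 − 0.5m.

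| m | Recorded rates | P(reject), 20 v 100 | P(reject), 20 v 20 |
|---|---|---|---|
| 10% | 55% v 45% | 13% | 8% |
| 20% | 60% v 40% | 39% | 22% |

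The nominal level is 5%. Errors in the opposite direction give 45% v 55% and 40% v 60%. Exchanging the labels open and closed leaves the test unchanged, so the rejection probabilities are the same. The illustration shows what differential misreading can do, not which way it would go.

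**The case against.** **The 3-month form can recover the status.** It repeats item 6 and carries dated fields for dehiscence and closure, and section 4.3.4.2 has wounds monitored for dehiscence under standard care. A reader might infer that any re-opening between an early 4-week visit and POD 30 is lost. The documents do not support that: a re-opening on day 29 has a dated field at the next scheduled visit. What remains is that this reconstruction is retrospective, and nothing directs staff to derive item 6 from the dates or to correct an earlier answer.

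**Under the wording of sections 6.1 and 6.3 the gap is smaller.** If the endpoint is closure at any time up to day 30, a closure seen on day 25 already settles it. This is a fair point. However, sections 2.1.1 and 5.1.1 and item 6 all specify status on POD 30, and section 5.2.4 gives durability as the reason. The two readings need to be reconciled.

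**The bias may run either way.** A reader might infer that early visits flatter tertiary closure while sparse notes penalise controls. That does not follow. With no coding rule, an indeterminate control could be coded closed as easily as open, and a tertiary wound open on day 23 but closed by day 30 would count against tertiary closure.

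**Frequency is unknown.** It would also go too far to call the control visits unscheduled, or to say that POD 30 status will often be unobserved. The plan simply does not give the control timing, and 7 of 11 counts permitted days, not visits.

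**A 30-day follow-up form may exist.** Section 7.0 lists one as Appendix G, but Appendix G is the SF-36 and the appendix list names no such form. It cannot be relied on as the answer.

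**Conclusion.** The point holds as a gap in how the primary endpoint is ascertained. It is not a defect of power. It is certain from the text that no visit is fixed at POD 30, that 7 of the 11 permitted days of the nearest visit precede it, that item 6 allows only Yes or No at every visit, and that no common rule covers the two groups. It follows that ascertainment can differ between groups. The documents establish neither how often this will matter nor in which direction.

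At the anticipated rates the significance test is robust, so a conclusion that the trial's test is invalid would not be supported. The exposure is in the two estimated proportions and their difference, which matter in a study whose stated aim (section 5.2.4) is to produce more quantitative data. Inference is also exposed if the true difference is much smaller than expected, more so with 20 controls. The sizes for indeterminate patients and for differential misreading rest on assumed counts and rates. This is a worthwhile, low-cost improvement.

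**What to change.** (a) Start the window of the assessment that supplies item 6 at POD 30, for example POD 30 to 35. Accept item 6 only from an examination on or after POD 30, and add a *not yet assessable* option for earlier forms.

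(b) Make the analysed endpoint a derived status, using one rule for form data and abstracted notes, applied in this order:

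1. If dated documentation (a closure or dehiscence date) settles the status on POD 30, use it.
2. Otherwise, *closed* means documented closed on or before POD 30 and still closed at the first examination on or after POD 30.
3. *Not closed* means open at the first examination on or after POD 30, with no documented closure before it.
4. Anything else is *indeterminate*, for example open before and closed after POD 30 with no closure date.

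(c) Analyse indeterminate patients once as closed and once as open, and report the range.

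(d) Align sections 6.1 and 6.3 with the POD 30 status endpoint. In the same edit, reconcile the control count (20 in section 2.1.1, 100 in section 6.1) and the 30-day form listed in section 7.0.

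**Cost.** There are no extra patients or visits. One visit moves by a few days, together with the SF-36 and adverse event evaluation done at it. One abstraction rule and one sensitivity analysis are added. Some patients, probably mainly controls, will be indeterminate, because a wound healing between notes seldom has an exact date. The difference would then be reported as a range instead of a single figure.
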